3.5.2.3 Long-term Overall Clinical Efficacy

PROPHYLAXIS AND ON-DEMAND TREATMENT

The long-term clinical efficacy of prophylaxis and/or on-demand treatment with Fanhdi, based on the hemostatic effect, and previous experience, will be determined by the investigator per standard of care utilizing a 4-point rating scale ("excellent," "good," "poor" or "no response" [Table 3-1, 25]) and collected. Efficacy data will be recorded in the appropriate eCRF and in the subject's source documents

FANHDI TREATMENT EXPOSURE

The extent of exposure to Fanhdi will be assessed as a long-term clinical efficacy variable. Information on the amount of Fanhdi (IU/kg) used per subject and per year and the amount of Fanhdi (number of IU/kg) used per infusion will be collected. Efficacy data will be recorded in the appropriate eCRF and in the subject's source documents

3.5.3 Subject Numbering

Within each study center, subjects in the study will receive a consecutive subject number. Subject numbers are generated beginning with the study center number (3 digits, assigned by the sponsor) followed consecutively with a unique number for each subject (4 digits, including leading zeros). For example, if the investigator's center number is 301, subject number will be 3010001, 3010002, 3010003, etc., in consecutive order. Subject numbers, once assigned, will not be reused at any center.

3.5.4 Data Collection Procedures

3.5.4.1 Data Sources

Data for this study will be obtained from medical records based on the information generated in the routine examinations and treatments that the investigator performs according to his or her standard medical practice. Approximately 15 subjects will be included for an observation period of 12 months.

3.5.4.2 Data Collection Procedures

The study data will be recorded and kept current in the eCRF and subject's source documents by the study center personnel directly responsible for the information. Entries made in the eCRF must be verifiable against source documents. The data in the eCRF will be monitored at the study center by Grifols representatives at regular intervals and reviewed for

completeness and compared with the source documents. Examples of acceptable source documents include individual subject medical records, prospective information gathered on source documentation worksheets, laboratory reports, and other diagnoses pertinent to this study which are separate from the eCRF. The listing of types of source documents which will be defined in the source data agreement will be filed in the Trial Master File.

All AEs and SAEs must be recorded in the eCRF and subject's source documents. All SAEs must be recorded on the SAE report form (see [Section 4.9.1](#)). The SAE report form must be kept in site records with a copy provided to the designated person as detailed in the study file.

3.5.5 Data Quality

At the completion of the study, all data will be transferred to Grifols according to The International Council for Harmonisation of Technical Requirements for Pharmaceuticals for Human Use (ICH) Good Clinical Practice (GCP) guidelines, local laws, regulations, and Grifols requirements. The study file must be kept until such time as the sponsor gives notice that they are to be destroyed.

The investigator must keep the study files. If an investigator moves, withdraws from an investigation, or retires, the responsibility for maintaining the files must be transferred to another person (eg, another investigator). Grifols must be notified in writing of the person responsible for maintaining the file and the notification must be kept in the sponsor study file and the investigator study center file.

4 PROCEDURES FOR ELICITING REPORTS OF AND FOR RECORDING AND REPORTING ADVERSE EVENT AND INTERCURRENT ILLNESSES

4.1 Warnings/Precautions

For complete information on Fanhdi, refer to the Summary of Product Characteristics [\(23\)](#).

4.2 Adverse Event Monitoring

Subjects must be carefully monitored for AEs. This monitoring includes clinical and laboratory tests and physical signs; any abnormalities judged by the investigator as clinically significant will be considered AEs. See [Section 4.3](#) for AE definitions. Adverse events should be assessed in terms of their seriousness, severity, and causal relationship to study treatment.

Adverse events will be elicited by spontaneous reporting by the study individual or by a non-leading inquiry or direct observation by the study staff.

All study subjects will be monitored after an AE until it is resolved. This monitoring includes clinical and laboratory tests and vital signs.

Adverse events and SAEs must be documented from signing of the ICF until the subject completes his or her final study visit, whether the subject completes the study or suspends participation early for any reason.

4.3 Adverse Event Definitions

4.3.1 Adverse Events

An AE is defined as any untoward medical occurrence in a subject or clinical investigation subject administered a medicinal product or study treatment and which does not necessarily have a causal relationship with this administration. An AE can therefore be any unfavorable and unintended sign (including any abnormal laboratory finding, for example), symptom, or disease temporally associated with the use of a medicinal product, whether or not considered related to the medicinal product.

4.3.2 Suspected Adverse Drug Reactions

All noxious and unintended responses to a medicinal product or study treatment related to any dose should be considered suspected ADRs. The phrase “responses to a medicinal product” means that a causal relationship between a medicinal product or study treatment and an AE is at least a reasonable possibility.

4.3.3 Thromboembolic Events

Subjects will be monitored for signs and symptoms of arterial and venous thromboembolic events per standard care. According to definitions in the International Classification of Diseases, Ninth Revision, Clinical Modification (ICD-9-CM), arterial and venous thromboembolic events include, but are not limited to deep vein thrombosis, pulmonary embolism, myocardial infarction, cerebrovascular accident, acute coronary syndrome, limb thrombosis, sagittal sinus thrombosis, and portal vein or mesenteric artery thrombosis.

All thromboembolic events will be recorded in the eCRF and subject’s source documents as an AE and reported accordingly.

4.4 Assessment of Causality of Adverse Event

The investigator is required to provide a causality assessment for each AE reported to the sponsor. The sponsor will consider the investigator’s causality assessment and also provide its own assessment.

Causal relationship to the study drug will be established according to medical judgment on whether there is a **reasonable possibility of a causal relationship between the AE and the study drug administration.**

The investigator must determine and classify the AE causality according to the following categories:

Unrelated/Not related: there is not a reasonable possibility of causal relationship between the AE and the study drug.

Possibly related: there is evidence to suggest a causal relationship between the study drug and the AE.

Definitely related: there is a reason to conclude that the study drug caused the AE.

Criteria to assess the causal relationship should take into account of the following conditions:

1. A plausible temporal sequence from the study drug administration to the AE onset
2. Whether the event follows a known response pattern to the suspected treatment
3. Whether the AE could be reasonably explained by the subject's clinical state, comorbidities, or concomitant medications
4. The occurrence of improvement on stopping/reducing the treatment (positive dechallenge) and/or reappearance of the event on repeated exposure (positive rechallenge).

For expedited safety reporting purposes, AEs assessed as either “definitively related” or “possible related” will be considered POTENTIALLY RELATED or just RELATED.

4.5 Severity of Adverse Event or Suspected Adverse Drug Reaction

Adverse events and suspected ADRs will be classified depending on their severity according to the following definitions:

Mild: an AE which is well tolerated by the subject, causing minimum degree of malaise and without affecting normal activities.

Moderate: an AE that interferes with the subject's normal activities.

Severe: an AE that prevents the subject from performing their normal activities.

Adverse event and suspected ADR severity gradation must be distinguished from an AE and suspected ADR seriousness gradation, which is defined according to event consequence. For example, headache can be mild, moderate or severe but not necessarily serious in all these cases.

The investigator will be responsible for assessing the AE and suspected ADR intensity during the clinical study, taking into account current criteria included in this section.

4.6 Expectedness of Adverse Event or Suspected Adverse Drug Reaction

An AE or suspected ADR is considered “unexpected” if the nature, seriousness, severity or outcome of the reaction(s) is not consistent with the reference information. The expectedness shall be determined by the sponsor according to the reference document (Summary of

Product Characteristics [23]) for any serious suspected ADRs (potentially related SAEs) for expedited safety reporting purposes.

4.7 Seriousness of Adverse Event or Suspected Adverse Drug Reaction

An AE or suspected ADR is considered “serious” if, in the opinion of either the investigator or sponsor, it results in any of the following outcomes:

- Death
- Life-threatening AE (life-threatening in the definition of “serious” refers to an event in which the subject was at risk of death at the time of the event; it does not refer to an event which hypothetically might have caused death if it were more severe)
- In-patient hospitalization or prolongation of existing hospitalization*
- A persistent or significant incapacity or substantial disruption of the ability to conduct normal life functions
- A congenital anomaly/birth defect
- An important medical event (important medical event in the definition of “serious” refers to those events which may not be immediately life-threatening, or result in death, or hospitalization, but from medical and scientific judgment may jeopardize the subject or/and may require medical or surgical or invasive intervention to prevent one of the other outcomes listed above).

*Hospitalization is to be considered only for hospital stays equal to or more than 24 hours. The following hospitalizations should not be reported as SAEs:

- Hospitalization or prolongation of hospitalization as part of a routine procedure followed by the center.
- Hospitalization for a survey visit, annual physicals, or social reasons.
- Elective or pre-planned hospitalizations for a pre-existing condition that had not worsened from Baseline (eg, elective or scheduled surgery or invasive procedure arranged prior to start of the study).
- Admissions not associated with an AE (eg, social hospitalization for purposes of respite care).

This definition permits either the sponsor or the investigator to decide whether an event is “serious”. If either the sponsor or the investigator believes that the event is serious, the event must be considered “serious” and evaluated by the sponsor for expedited reporting.

4.8 Adverse Event Documentation

All AEs and SAEs occurring after the subject has **signed the ICF through the final study visit** (ie, last day of the subject’s participation in the clinical study, whether the subject completes the study or participation is suspended early for any reason) must be fully recorded

in the subject's eCRF, source documents, and SAE report form (if serious) as well as in the medical record. If no AE has occurred during the study period, this should also be indicated in the eCRF.

It is the responsibility of the investigator to ensure that all AEs (either serious or non-serious) are appropriately recorded in the eCRF and subject's source documents in a timely manner (up to 5 calendar days upon being made aware of AE occurrence).

At each visit, AEs will be elicited by asking the individual a non-leading question such as "Do you feel different in any way since the last visit?" Moreover, AEs will also be collected through directly observed events or spontaneously volunteered by the subject. Clearly related signs, symptoms and abnormal diagnostic procedures should preferably be grouped together and recorded as a single diagnosis or syndrome wherever possible.

The following variables must be recorded in the AE eCRF and source documents:

- The verbatim term (a diagnosis is preferred)
- Date/time of onset
- Date/time of resolution
- Severity (mild, moderate, severe)
- Causality (unrelated, possibly related, definitely related)*
- Seriousness (yes, no)
- Action taken (with regard to study treatment)
- Other action (to treat the event)
- Outcome and sequel (follow-up on AE)

*Causality assessment will be made only when the AE occurs after the subject has initiated at least one infusion of the study drug. An AE occurring before subject's exposure to study treatment will be always labeled as "unrelated/not related".

For AEs that occur during infusions, the time of onset of the AE, and the time of AE change materially in intensity (recorded as a separate AE), and/or resolve will be captured in the eCRF.

In addition to the investigator's own description of the AEs, each AE will be encoded according to the Medical Dictionary for Regulatory Activities (MedDRA®).

For example, a laboratory test abnormality considered clinically significant, eg, causing the subject to withdraw from the study, requiring treatment or causing apparent clinical manifestations, or judged clinically significant in the context of the subject's medical history by the investigator, should be reported as an AE. Each event must be described in detail along with start and stop dates, severity, relationship to study drug, action taken and outcome. Each event must be adequately supported by documentation as it appears in the subject's medical or case file.

4.9 Reporting of Adverse Events

4.9.1 Reporting of Serious Adverse Events

Any SAE that occurs after **signing the study ICF through the final study visit** (ie, last day of the subject's participation in the clinical study, whether the subject completes the study or participation is suspended early for any reason) must be expeditiously reported. Each SAE must be fully recorded in the subject's eCRF, source documents, and SAE Report Form.

All SAEs will be reported using the designated SAE Report Form. When the investigator becomes aware of a SAE, she/he must submit a completed, signed and dated SAE Report Form (in English) **within 24 hours** to the sponsor by email/fax. The date of this SAE discovery by the site staff should be documented in the source documents (ie, medical records).

Each SAE must be followed up until resolution or stabilization. After the initial report, all relevant information for SAE follow-up, and for the outcome, must also be supplied to the sponsor in a timely manner (within 3 days from its identification or within 24 hours for relevant new information) by means of the SAE Report Form. In addition, the sponsor or contract research organization may request additional information and/or reports.

All SAE Report Forms must be reported to:

Grifols Global Pharmacovigilance

Email: [contact]

FAX (back-up only): [name]

When required, and according to local law and regulations, SAEs must be reported to the Ethics Committee (EC) and regulatory authorities. Copies of the investigator's reports must be sent to the sponsor.

4.9.2 Reporting of Non-serious Adverse Events

While investigators are not requested to expeditiously send non-serious AEs to the sponsor with the 24 hour timeframe; they are requested to record them in the eCRF in a timely manner (up to 5 calendar days upon being made aware of AE occurrence). The sponsor will periodically monitor AE records and request additional information from the site if the event meets criteria for a suspected ADR. In the event of a suspected ADR the investigator may be asked to provide additional information to Grifols Global Pharmacovigilance, if necessary. When required, and according to local law and regulations, suspected ADRs must be reported to the EC and regulatory authorities. Copies of the investigator's reports must be sent to the sponsor.

4.9.3 Reporting Pregnancy

While pregnancy itself is not a true “AE,” pregnancy occurring in a clinical study must be followed, to collect information regarding the experiences of gestation and pregnancy with study drug exposure. The investigator must report any pregnancy that occurs in a female study subject or partner of a male study subject subsequent to informed consent until 28 days after the last dose of study drug.

A pregnancy not verified before the Baseline Visit but occurring during the course of the study will be not considered an AE, unless a relation to the study drug is suspected. In any case, a *Pregnancy Report Form* must be completed and sent as soon as possible to the sponsor. A copy of the form should be filed at the study site for follow-up until the end of the pregnancy. Any pregnancy must be followed by the investigator until delivery or to the end of pregnancy. Any anomalies, complications, abnormal outcomes, or birth defect observed in the child must be reported as a SAE within 24 hours of the investigator or study personnel’s first knowledge.

4.10 Type and Duration of the Follow-Up of Subjects after Adverse Events/Non-Serious Suspected Adverse Drug Reactions

In so far as is possible, all individuals will be monitored until the SAE/ non-serious suspected ADR is resolved. If a SAE/ non-serious suspected ADR is active or in process when the subject completes the study, the course of the event must be monitored until the final result is known or the event has stabilized and no additional changes are expected and the investigator decides that further monitoring is not necessary.

The sponsor must be notified if the investigator performs or conducts additional studies (in a manner not required by the protocol) in order to determine the nature and/or causality of the SAE/non-serious suspected ADR.

New relevant information regarding a SAE/non-serious suspected ADR must be recorded in a follow-up report. The updated or corrected information must also be recorded in the revised eCRF and in the subject’s source documents.

5 STATISTICAL ANALYSIS

Unless otherwise specified, descriptive statistics will include the number of non-missing observations, mean, standard deviation (SD), median, minimum, and maximum values for the continuous/quantitative data or absolute and relative frequency counts and percentages for categorical/qualitative data.

Data handling and evaluation procedures will be described in the Statistical Analysis Plan.

5.1 Population for Statistical Analyses

The Safety population will include all subjects enrolled in the clinical study and will be used for all safety and efficacy analyses.

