3 STUDY DESIGN

3.1 Study Design and Plan

This is a Phase 4, observational, multi-center, prospective, post-authorization cohort study examining the safety (immunogenicity and thrombogenicity) and overall clinical efficacy of long term use of Fanhdi in routine clinical practice in approximately 15 subjects with VWD. In this clinical study, subjects will be treated with Fanhdi according to the investigator's standard of care to achieve hemostasis. Enrolled subjects will be treated with Fanhdi as their sole source of VWF/FVIII concentrate for prophylaxis and treatment of all bleeding episodes and surgical or invasive procedures for an observational period of 12 months.

Data will be collected from the information generated during routine examinations and treatments as performed by the investigator per standard of care during an observation period of 12 months, starting with the first Fanhdi infusion. There will be no intervention with the prescribing habits or practices of the investigator's standard of care, however the investigator is expected to treat the subject within the approved labeling for dose and frequency of Fanhdi as described in [Section 3.1.1 \(23\)](#). Data collection for all subjects will include inhibitor development (immunogenicity), thrombogenicity, adverse events (AEs), bleeding episodes (spontaneous or traumatic bleeding), surgery or invasive procedure, duration and severity, assessment and achievement of hemostasis, and Fanhdi consumption. Data will be transcribed into electronic case report forms (eCRFs) by designated study center personnel.

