3.2 Selection of Study Population

3.2.1 Inclusion Criteria

A subject who will be treated with Fanhdi must meet all the following inclusion criteria to be eligible for participation in this study:

1. Male or female subjects ≥ 18 years of age diagnosed with hereditary VWD of any type and severity who require replacement therapy with VWF/FVIII concentrates when desmopressin (DDAVP) treatment alone is ineffective or contra-indicated.
2. Subjects with a history of receiving prior treatment with VWF concentrates due to bleeding episodes and/or surgery or invasive procedures (on demand or prophylaxis).
3. Subjects who are expected to experience bleeding episodes and/or surgeries or invasive procedures (including elective surgeries) requiring replacement therapy in the future or with active bleeding at the time of inclusion.
4. Subjects who are willing and able to provide written informed consent or have an authorized representative able to provide written informed consent on behalf of the subject in accordance with local law and institutional policy.

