5.3.1 Adverse Events

Safety analysis will be primarily focused on a descriptive analysis of suspected ADRs. Safety assessment will be based on the prevalence of suspected ADRs that occurred during the clinical study.

Adverse events will be coded and classified using MedDRA terms (system organ class [SOC] and preferred term [PT]).

Adverse events will be classified as treatment-emergent AEs (TEAEs) or non-treatment-emergent AEs (non-TEAEs) depending on the comparison of AE onset date/time with the start date/time of study treatment after the subject joins the study. A TEAE will be defined as an AE which occurs between the beginning of the first infusion of study treatment after the subject joins the study and the final visit of the clinical study. A non-TEAE will be defined as an AE which occurs prior to the start of study treatment after the subject joins the study. Non-TEAEs and TEAEs will be summarized separately.

All AEs will be summarized by presenting subject incidences and percentages, and they will also be listed by subject and by SOC.

In addition, TEAEs, including suspected ADRs, will be summarized by SOC, PT, causal-relationship, intensity (severity) and seriousness (serious vs non-serious) using descriptive statistics. Each subject will only be counted once at each level of SOC or PT. For the summary by severity or causality, a subject will only be counted once per SOC or PT using the most severe AE or the AE with the strongest causal relationship to study treatment.

Adverse events temporally associated to the infusion of study treatment (ie, infusional AEs, including infusional suspected ADRs), will be summarized by presenting infusion/subject incidences and percentage and ordered by ordinal number of infusions, and listed. Temporally associated AEs occurring during study drug infusion or within 24 hours post the end of study drug infusion, and occurring during or within 72 hours post the end of study drug infusion will be summarized separately.

Subjects with a SAE or who withdraw from the study because of an AE will also be individually listed and summarized.

5.3.2 Clinical Laboratory Values Including Inhibitor (Immunogenicity) and Functional Activity Testing

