5.5 Study Size Determination

Approximately 15 subjects are planned to be enrolled in this clinical study. The sample size is based on clinical considerations and was not formally calculated.

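### The Safety population has no exposure condition, so any enrolled but never-infused subject would dilute the per-subject TEAE, suspected ADR and thromboembolic percentages

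*Protocol*

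**What the plan says.** Section 5.1 of the protocol, repeated in the synopsis under Statistical Methods, defines one population: "The Safety population will include all subjects enrolled in the clinical study and will be used for all safety and efficacy analyses". It names no second population and no minimum exposure.

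Other sections bear on whether enrolment implies exposure:

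- Section 3.2.1, criterion 3, admits "Subjects who are expected to experience bleeding episodes and/or surgeries or invasive procedures (including elective surgeries) requiring replacement therapy in the future", with no time limit. Active bleeding at inclusion is only the alternative.
- Section 3.1 starts data collection at exposure: "during an observation period of 12 months, starting with the first Fanhdi infusion".
- Section 3.5.1.1 records AEs from signature of the consent form.
- Section 5.3.1 gives pre-infusion events their own class: "A non-TEAE will be defined as an AE which occurs prior to the start of study treatment after the subject joins the study".
- Section 3.2.3 allows withdrawal at the subject's request or for ineligibility. Neither reason presupposes an infusion.
- Section 3.1 also states an intention: "Enrolled subjects will be treated with Fanhdi as their sole source of VWF/FVIII concentrate".

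On reporting, Section 5.3.1 says "All AEs will be summarized by presenting subject incidences and percentages" and makes suspected ADRs the main focus of the safety analysis. Section 5.5 says "Approximately 15 subjects are planned to be enrolled in this clinical study".

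**The concern.** The population that serves as denominator should consist of subjects who could have had the event. Under Section 5.3.1 a TEAE cannot occur before the first infusion. Under Section 4.8 an AE before exposure is always classed as unrelated, so it cannot be a suspected ADR as Section 4.3.2 defines one. An enrolled subject who is never infused therefore adds one to the denominator and can add nothing to the numerator.

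The error runs one way: it lowers the apparent risk of the product. It falls on the main safety output of a study that, according to Section 1.2, a regulator requested, and thrombogenicity is one of the two named parts of the safety objective (Section 2.1). With about 15 subjects, each misplaced subject shifts the percentages visibly.

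**Working it through.** **Plan's own figure.** There is none to reproduce. The protocol states no error rate, power or effect size: "The sample size is based on clinical considerations and was not formally calculated".

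**Inputs.** N = 15 enrolled (Section 5.5). u = number enrolled but never infused; the protocol does not give it, so 0 to 5 is assumed. x = number of infused subjects with the event.

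**Step 1: dilution of a per-subject percentage.** Among exposed subjects the proportion is x/(15-u). Under Section 5.1 it is reported as x/15. The ratio of reported to exposed is (15-u)/15, whatever x is.

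**Step 2: zero events.** The exact two-sided 95% upper bound with no events in n subjects is 1 - 0.025^(1/n). For n = 15 this is 21.8%. The protocol plans no confidence intervals, so these bounds only show how much reassurance an absence of events would carry.

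| u | infused | factor (15-u)/15 | one affected subject: reported vs among infused | zero events, upper bound: on 15 vs on infused |
|---|---|---|---|---|
| 0 | 15 | 1.00 | 6.7% vs 6.7% | 21.8% vs 21.8% |
| 1 | 14 | 0.93 | 6.7% vs 7.1% | 21.8% vs 23.2% |
| 3 | 12 | 0.80 | 6.7% vs 8.3% | 21.8% vs 26.5% |
| 5 | 10 | 0.67 | 6.7% vs 10.0% | 21.8% vs 30.8% |

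**Step 3: which outputs have enrolled subjects as denominator.**

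- *Exposed to dilution:* subject incidences of TEAEs and suspected ADRs (Section 5.3.1), and of treatment-emergent thromboembolic events, which are recorded as AEs (Sections 4.3.3 and 5.3.3).
- *Not exposed:* the proportions rated good or excellent, which are per bleeding episode or per procedure (Section 5.4); the per-infusion part of the infusional AE summary (Section 5.3.1); bleed duration, which is timed from the first infusion (Section 3.5.2.1); and inhibitor, laboratory, vital-sign and examination results, which are listed by subject (Sections 5.3.2, 5.3.4 and 5.3.5). A never-infused subject contributes no infusion and no Fanhdi-treated episode, so the factor for the episode and infusion rates is 1.00.
- *Conditional:* infusions, exposure days, dose per month and bleed counts (Section 5.4) are pulled down only if zeros are entered for untreated subjects. Section 5 bases continuous summaries on non-missing observations and prescribes no zeros. The long-term efficacy rating is diluted only if unrated subjects stay in its denominator, which the protocol does not say.

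**The case against.** The strongest reply is that the protocol describes its participants as treated. Section 3.1 says enrolled subjects will receive Fanhdi, Section 3.2.1 addresses eligibility to a subject who will be treated with it, and Section 3.5.4.1 includes about 15 subjects for a 12-month period that begins at the first infusion. Criterion 2 also requires earlier treatment with VWF concentrate. The separate class of pre-infusion AEs shows a gap between joining and first infusion; it does not show that anyone is never infused. All of this stands. It makes u unknown and possibly zero. It does not supply the missing condition, because an intention to treat everyone is not a rule for the analysis set when someone is not treated.

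A reader might infer that untreated subjects dilute every safety and efficacy result, including inhibitor incidence and mean exposure. The documents do not support that. The efficacy proportions count episodes or procedures. Section 5.3.2 plans inhibitor listings, and the only inhibitor incidence mentioned (Section 3.5.1.2) is indexed to the number of exposures. A subject with no observation period has an undefined dose per month, not a zero.

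It is also fair to say that the study is descriptive, tests no hypothesis and lists AEs by subject, so a careful reader could recalculate the percentages. That lowers the severity. The headline percentages would still be wrong as printed.

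**Conclusion.** The point holds in a limited form. Section 5.1 fixes a population without an exposure condition, and the protocol's own entry, withdrawal and AE rules allow a subject to be in it without ever receiving Fanhdi. Each such subject lowers the per-subject TEAE, suspected ADR and thromboembolic percentages, always in the favourable direction. The relative understatement is u/15: none at u=0, 7% at u=1, 20% at u=3 and 33% at u=5.

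The size rests entirely on the assumed u; the protocol gives no basis for any particular value, and the range assumes exactly 15 enrolled. This is not a defect in the efficacy proportions, the per-infusion rates or the inhibitor listings. It is a wording error with a known direction and uncertain size, worth correcting because it touches the main safety output.

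**What to change.** In Section 5.1 and the synopsis, define the Safety population as enrolled subjects who receive at least one Fanhdi infusion after joining the study. Use it for the TEAE, suspected ADR, thrombogenicity, exposure and efficacy summaries. Keep all enrolled subjects for disposition and for AEs that occur before the first infusion, and report the number enrolled but never infused. Any statistical analysis plan should carry the same definition.

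The cost is a small text change in two places. Denominators may be slightly smaller and percentages slightly less favourable. If every enrolled subject is infused, nothing changes.
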